9.7.3. Sensitivity analysis

9.7.3.1. Risk interval misspecification

The SCRI design approach proposed in this protocol requires that risk intervals be specified correctly. If risk intervals are too long, comparative risk estimates may be attenuated. A sensitivity analysis with alternative risk interval definitions will be considered for general safety events if signals are observed in other studies or surveillance systems and if the risk interval is not well characterized.

9.7.3.2. Exposure misclassification

In the analysis of pregnancy and birth outcomes, the potential for lack of recording of COVID-19 vaccines in claims and electronic health records during the exposure window may lead to misclassification of exposed individuals as “unexposed” individuals, which will bias comparative risk estimates. If feasible, a sensitivity analysis will be considered to restrict analyses among data RPs that have linkages to high-quality immunization registry data available for some or all of their population. Additionally, quantitative bias analysis of comparative risk estimates of pregnancy and birth outcomes will be considered to assess the potential impact of exposure misclassification. If such analysis is performed, external vaccine coverage rates and estimates for sensitivity and specificity of COVID-19 vaccine capture in

claims data (based on the published literature if available, or a plausible range) will be used to obtain comparative risk estimates corrected for exposure misclassification.

9.7.3.3. Confounding

Comparisons between vaccinated and unvaccinated pregnant women may be confounded, as unvaccinated women may differ substantially with respect to health-seeking behaviors and other risk factors for pregnancy and birth outcomes. For pregnancy and birth outcomes, a sensitivity analysis will be performed among pregnant women with a recorded history of monovalent COVID-19 vaccination before cohort entry, which may serve as a proxy for these health-seeking behaviors. This sensitivity analysis will also address potential misclassification of unexposed status, as women with a recorded history of monovalent COVID-19 vaccination may have more complete data on bivalent COVID-19 vaccination.

Confounding by time-invariant characteristics is not a concern in the SCRI design because it is self-controlled.

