7. RATIONALE AND BACKGROUND

On 31 August 2022, the US FDA authorized Pfizer-BioNTech bivalent COVID-19 Vaccine (Original and Omicron BA.4/BA.5) for emergency use as a single booster dose for the prevention of COVID-19 (coronavirus disease 2019) in individuals aged 12 years and older (FDA, 2023b). On 12 October 2022, the FDA subsequently authorized the vaccine for use as a single booster dose in individuals aged 5-11 years. Additionally, on 08 December 2022, the FDA authorized Pfizer-BioNTech bivalent COVID-19 Vaccine to be used as a third dose in the primary series in children aged 6 months through 4 years, following 2 doses of Pfizer-BioNTech monovalent COVID-19 Vaccine (Original). On 14 March 2023, the FDA authorized Pfizer-BioNTech bivalent COVID-19 Vaccine for use as a single booster dose in children aged 6 months through 4 years who had previously completed a 3-dose primary series of Pfizer-BioNTech monovalent COVID-19 Vaccine (FDA, 2023a).

PFIZER CONFIDENTIAL

CT24-WI-GL02-RF02 4.0 Non-Interventional Study Protocol Template For Secondary Data Collection Study

01-Jun-2022

Page 20 of 62

On 18 April 2023, the FDA amended the EUA for Pfizer-BioNTech COVID-19 Vaccine to simplify the vaccination schedule, such that the current bivalent vaccine was to be used for all initial and subsequent doses administered to individuals aged 6 months and older. At the same time, the original Pfizer-BioNTech monovalent COVID-19 Vaccine was no longer authorized for use (FDA, 2023b). Updates to simplify the vaccination schedule were as follows:

- For unvaccinated individuals, Pfizer-BioNTech bivalent COVID-19 Vaccine was authorized as a 3-dose series in individuals aged 6 months through 4 years and as a single dose in individuals aged 5 years and older.
- For individuals aged 6 months through 4 years who had previously received 1 dose of monovalent vaccine, Pfizer-BioNTech bivalent COVID-19 Vaccine was authorized to be used as 2 additional doses; for individuals aged 6 months through 4 years who had received 2 or 3 doses of monovalent vaccine, Pfizer-BioNTech bivalent COVID-19 Vaccine was authorized to be used as a single dose.
- For individuals aged 5 years and older who had previously received 1 or more doses of monovalent COVID-19 vaccine, a single dose of Pfizer-BioNTech bivalent COVID-19 Vaccine was authorized.

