As of 11 September 2023, the Pfizer-BioNTech bivalent COVID-19 Vaccine (Original and Omicron BA.4/BA.5) is no longer authorized for use in the US (since the updated [2023–2024 Formula] COVID-19 Pfizer-BioNTech COVID-19 Vaccine became available) (Regan et al., 2023). Since the authorization of Pfizer-BioNTech bivalent COVID-19 Vaccine, no safety signal for myocarditis/pericarditis has been observed with this vaccine in any age group in the VSD, with preliminary data suggesting lower rates of myocarditis/pericarditis following booster vaccination with Pfizer-BioNTech bivalent COVID-19 Vaccine compared with rates of myocarditis/pericarditis following receipt of Pfizer-BioNTech monovalent COVID-19 Vaccine among individuals aged 12-39 years (Shimabukuro, 2023). While a potential safety signal for ischemic stroke for individuals aged 65 years and older was initially observed in the VSD, the signal was not subsequently confirmed (Shimabukuro, 2023).

Post-authorization observational studies using real-world data are still needed among the general population and among subpopulations of interest (eg, pregnant people, immunocompromised individuals, and the pediatric population) to assess the association between Pfizer-BioNTech bivalent COVID-19 Vaccine and pre-determined safety events of interest, including myocarditis/pericarditis. This protocol describes a proposed observational study of safety events of interest, including myocarditis/pericarditis, occurring in recipients of the Pfizer-BioNTech bivalent COVID-19 Vaccine using claims data and electronic health records data (where available) from data RPs participating in the FDA Sentinel System.

This non-interventional study is designated as a Post-Authorization Safety Study (PASS) and is a commitment to the US FDA and is also a RMP Category 3 commitment to the EMA.

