All individuals receiving Pfizer-BioNTech bivalent COVID-19 Vaccine will be assumed to have met the eligibility criteria to receive the vaccine under the FDA authorization (see Section 7 for summary of FDA authorizations of Pfizer-BioNTech bivalent COVID-19 Vaccine, which have changed over the course of the study period). This assumption will be made because requiring the prerequisite number and types of COVID-19 vaccine doses before receipt of Pfizer-BioNTech bivalent COVID-19 Vaccine is anticipated to require health plan enrollment from the date of an individual's initial eligibility for COVID-19 vaccination, which would severely reduce the number of individuals eligible for the study and potentially lead to imprecise comparative risk estimates and selection bias.

Given the FDA authorizations of Pfizer-BioNTech bivalent COVID-19 Vaccine, it is anticipated that some individuals may contribute more than 1 dose of Pfizer-BioNTech bivalent COVID-19 Vaccine to the analyses. Details on how subsequent doses of Pfizer-BioNTech bivalent COVID-19 Vaccine will be handled in the analysis will be described in the SAP.

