9.3.3. Covariates

Table 7 presents variables that will be used for descriptive analysis in analyses of general safety events as well as variables that will be used for descriptive analysis, matching, and

090177e19f732934\Approved\Approved On: 14-Dec-2023 13:35 (GMT)

propensity score estimation in analysis of pregnancy and birth outcomes. These variables will be identified using claims or electronic health records data (where available).

Table 7. Covariates used for descriptive analysis, matching or propensity score estimation

Variable	General safety events	Pregnancy and birth outcomes		
	Descriptive	Descriptive	Matching	Propensity scores
Age (as of the index date or LMP ^a)	X	X	X	
Sex	X			
Geographic region (based on the most recent information at the time of data refresh)	X	X	X	
Immunocompromising conditions (in the 12 months before the index date) 
 Including immunodeficiencies, immunosuppressant medication use, HIV and other immunosuppressing conditions, and receipt of organ or bone marrow transplants 	X	X		X
Pregnancy status as of the index date	X			
History of severe COVID-19 disease (as of the index date) 
 Defined with inpatient diagnoses in the principal diagnosis position or in pregnant women, with inpatient claims with a principal diagnosis of viral diseases complicating pregnancy and a diagnosis of COVID-19 in another position 	X	X		X
Receipt of the index Pfizer-BioNTech COVID-19 bivalent Vaccine as a primary series dose vs booster dose; only to be assessed if feasible to identify in the data sources; anticipated to be incomplete	X	X		
Other vaccines recommended for routine use (on the index date or from 28 days before pregnancy until end of pregnancy) ^b	X	X		X
Estimated pregnancy start date (LMP)		X	X	
Gestational age on the index date ^c		X		

090177e19f732934\Approved\Approved On: 14-Dec-2023 13:35 (GMT)

Table 7. Covariates used for descriptive analysis, matching or propensity score estimation

Variable	General safety events	Pregnancy and birth outcomes		
	Descriptive	Descriptive	Matching	Propensity scores

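### Recorded COVID-19 vaccination before the exposure window is in neither the matching set nor the propensity score of the primary pregnancy and birth outcome analyses, only in a sensitivity restriction

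*Protocol*

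**What the plan says.** **Primary control of confounding.** Protocol Sections 9.1, 9.2.2 (Table 1), 9.2.3 (Table 2) and 9.7.2 match exposed to unexposed women on pregnancy start, maternal age and state or region. For pregnancy outcomes, gestational age at entry is aligned through the index date. All other confounding is left to inverse probability weighting, using the propensity-score column of Table 7, titled "Covariates used for descriptive analysis, matching or propensity score estimation". No row marked for matching or propensity scores is prior COVID-19 vaccination. The nearest row, whether the index bivalent dose was primary series or booster, is descriptive only and has no meaning for an unexposed woman.

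**Comparators.** Tables 1 and 2 require only that an unexposed woman had no COVID-19 vaccine in the exposure window. Never-vaccinated women therefore qualify.

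**Where prior vaccination is used.** Section 9.7.3.3 states that "a sensitivity analysis will be performed among pregnant women with a recorded history of monovalent COVID-19 vaccination before cohort entry", as a proxy for health-seeking behavior. The Abstract, Table 10 and Section 9.9 repeat this restriction.

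**Who could receive the dose.** Section 7 reports that on 31 August 2022 the FDA "authorized Pfizer-BioNTech bivalent COVID-19 Vaccine (Original and Omicron BA.4/BA.5) for emergency use as a single booster dose" at ages 12 and over. It continues: "On 18 April 2023, the FDA amended the EUA for Pfizer-BioNTech COVID-19 Vaccine to simplify the vaccination schedule". Unvaccinated people could then receive it, in a 3-dose series for the youngest children "and as a single dose in individuals aged 5 years and older". Finally, "As of 11 September 2023, the Pfizer-BioNTech bivalent COVID-19 Vaccine (Original and Omicron BA.4/BA.5) is no longer authorized for use in the US". Section 9.2.1.1, written for the general safety population, says recipients "will be assumed to have met the eligibility criteria to receive the vaccine under the FDA authorization".

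**The concern.** The protocol treats prior COVID-19 vaccination as a confounder in its own reasoning. Sections 9.1 and 9.9 credit the self-controlled design with removing confounding by vaccination history, and Section 9.7.3.3 accepts that unvaccinated pregnant women may differ in health-seeking behavior and other risk factors. The cohort contrast, which serves primary objectives 2 and 3, then has no control for that variable.

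It is also more than an ordinary confounder here. For most of the authorization period, a prior dose was a condition for receiving the exposure. Exposed women indexed in that period should nearly all be previously vaccinated, while their comparators may be any mix of ever- and never-vaccinated. The headline hazard ratios and prevalence odds ratios may therefore carry that difference. If previously vaccinated women have lower outcome risk for other reasons, a modest harm could be hidden or a null effect could look protective.

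**Working it through.** **1. Booster-only share of the authorization (dates from Section 7).**
- 31 August 2022 to 18 April 2023: 230 days.
- 31 August 2022 to 11 September 2023: 376 days.
- 230 / 376 = 61% of calendar time. The documents do not give the share of doses.

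**2. The protocol's own power figure (Section 9.5.2, Table 9).** For stillbirth the inputs are incidence 0.5%, 100,000 women per group, hazard ratio 1.2 and two-sided alpha 0.05; stated power is 0.851.
- Expected events: 100,000 × 0.005 × (1 + 1.2) = 1,100.
- Schoenfeld: Φ(√1,100 / 2 × ln 1.2 − 1.96) = 0.856.

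The stated figure reproduces closely. It assumes no confounding, so it does not bear on whether the contrast is biased.

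**3. Illustrative bias from leaving out a binary confounder.** None of these inputs is in the documents; all are assumptions. Prior vaccination is taken as about 100% in exposed women and p0 in comparators, with outcome risk ratio RR for previously vaccinated versus not. With no adjustment through other covariates:

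B = RR / (p0 × RR + 1 − p0)

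| p0 | RR | B | True HR 1.2 reads |
|---|---|---|---|
| 0.4 | 0.8 | 0.8 / 0.92 = 0.870 | 1.04 |
| 0.6 | 0.8 | 0.8 / 0.88 = 0.909 | 1.09 |
| 0.8 | 0.9 | 0.9 / 0.92 = 0.978 | 1.17 |

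A wider grid uses B = [pE × RR + 1 − pE] / [pU × RR + 1 − pU], with pE (exposed) 80-100%, pU (unexposed) 30-70% and RR 0.7-0.9. It gives B from 0.77 to 0.99, so a true hazard ratio of 1.2 would read 0.92 to 1.19.

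**4. What B = 0.90 would do, at the protocol's own sizes.**
- Stillbirth, 100,000 per group: apparent hazard ratio 1.2 × 0.90 = 1.08; events 100,000 × 0.005 × 2.08 = 1,040; power falls from about 0.86 to about 0.24.
- Preterm birth, 20,000 per group, incidence 10%, no true effect: events 20,000 × 0.10 × 1.90 = 3,800; the test would reject in favor of apparent protection about 90% of the time.

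**The case against.** **The protocol already recognizes this.** Section 9.7.3.3 names the confounding and commits firmly to the restricted analysis. The primary analysis also follows the stated comparator, no COVID-19 vaccine during pregnancy. This stands: a reader might infer an oversight or an internal contradiction, and there is neither. The fault is one of placement, since the primary estimates lack control that the sensitivity analysis has.

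**Recorded history is incomplete.** Section 9.9 says only 47% of people in the Sentinel database have at least 2 years of enrollment, the cohorts require only 12 months, and doses given without reimbursement may not be recorded. This also stands, and it limits what adjustment can do. It does not justify leaving the variable out: the same recorded history is judged usable for the restriction, and Table 7 keeps obesity, alcohol and smoking in the propensity score despite expecting incomplete capture.

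**The propensity score contains proxies.** Healthcare utilization, other routine vaccines and comorbidities will absorb part of the difference, so the factors above are unadjusted and not the residual bias after weighting. But none of these determined eligibility for the dose.

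**The SAP may change the model.** Section 9.7 allows that. However, Table 7 assigns each variable's role, and Section 9.7.3.3 gives this one a sensitivity role. That is a stated choice that needs changing.

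**Conclusion.** The omission is confirmed, and the primary estimates for objectives 2 and 3 may be confounded by it. How much is not known from the documents. The range of 0.87-0.98 (a true hazard ratio of 1.2 reading 1.04-1.17) depends entirely on assumed prevalences and risk ratios, before any adjustment through proxies.

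Three stronger readings are tempting but unsupported:
- **That the bias must run downward and hide harm.** This is the likely direction if vaccinated women are healthier or seek more care, but Section 9.7.3.3 says only that comparisons may be confounded.
- **That 61% of exposed women received a booster-only dose.** The figure counts days, not doses.
- **That never-vaccinated comparators could never have been exposed.** This holds under the authorization only before 18 April 2023. Pregnancies spanning that date had eligible time within the longer exposure windows, such as those for stillbirth and small size for gestational age.

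**What to change.** Add recorded COVID-19 vaccination before the exposure window (any versus none, from all available data) to the matching variables in Tables 1, 2 and 7 for the primary pregnancy and birth outcome analyses. Amend Section 9.7.2 to agree. Keep the restriction to women with recorded monovalent history as the sensitivity analysis.

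Matching is preferable to a propensity-score term alone. For index dates before 18 April 2023, prior vaccination nearly determines exposure, so exposed women whose earlier doses went unrecorded could receive extreme weights.

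**Cost.** No new data source is needed, because recorded monovalent history is already planned for the restriction; the cut-off must be set at the start of the exposure window. Section 6 expects the final-analysis query in the second quarter of 2026. Number of doses and time since last dose would be optional extra derivations.

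**Downside.** Control stays partial: an exposed woman with unrecorded earlier doses would be matched to a comparator with no recorded history, who may be truly never-vaccinated. Some exposed women may also be harder to match, so the report should give the number unmatched.

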9.7.3.4. Outcome misclassification

Outcome misclassification is possible due to the use of claims and structured electronic health records to identify safety events of interest. If the performance of the algorithm for myocarditis/pericarditis has not been demonstrated to be adequate in prior validation studies, quantitative bias analysis (as described in Section 9.3.2) will be performed on comparative risk estimates for myocarditis/pericarditis using algorithm validation results from Study C4591009 if the results are applicable to this study; if the results from Study C4591009 are not applicable to this study, then algorithm validation results from other studies may be used.

Quantitative bias analysis of comparative risk estimates for other study outcomes may be considered if safety signals are observed in other surveillance systems or studies.

9.7.4. Secondary objectives (subgroups of interest)

Subgroup analysis of general safety events will be conducted among pregnant women, immunocompromised individuals, individuals with a recorded history of severe COVID-19 (defined as an inpatient diagnosis in the principal diagnosis position, or in pregnant women, an inpatient claim with a primary diagnosis of viral diseases complicating pregnancy and diagnosis of COVID-19 in another position), and among subgroups defined by age. For myocarditis/pericarditis, age will be categorized as 6 months through 4 years, 5-11, 12-17, 18-24, 25-29, 30-39, 40-49, 50-64, and ≥ 65 years. For all other general safety events, age will be categorized as 6 months through 4 years, 5-11, 12-17, 18-64, and ≥ 65 years. Additionally, if at least 5 events are observed in a given subgroup, analysis for myocarditis/pericarditis will be performed in subgroups defined jointly by sex and age (in the above categories).

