9. RESEARCH METHODS

9.1. Study design

The study will use a SCRI design to assess general safety events (ie, non-pregnancy related safety events of interest, including myocarditis/pericarditis; see Section 9.3.2.1 for list of specific events) among the general population and specific subpopulations of interest (immunocompromised individuals, pregnant women, and the pediatric population). A cohort design will be used to assess pregnancy and birth outcomes.

For general safety events, the SCRI design (Figure 1) will compare the incidence of safety events of interest in a predefined post-vaccination risk interval with that in a self-matched post-vaccination control interval, among individuals who have received Pfizer-BioNTech bivalent COVID-19 Vaccine. A buffer period (in which incidence will not be assessed) will be incorporated between the risk and control intervals to avoid any carry over effects from the risk interval into the control interval. Control intervals for each outcome will be defined to reflect the baseline risk of the outcome, and buffer and control intervals will take into consideration the duration of the risk interval, potential seasonality of the outcome, and the recommended timing between the initial bivalent vaccine dose and additional COVID-19

[figure not shown]
PFIZER CONFIDENTIAL

CT24-WI-GL02-RF02 4.0 Non-Interventional Study Protocol Template For Secondary Data Collection Study
01-Jun-2022

Page 23 of 62

vaccine doses. Additionally, as an eligibility criterion for each specific safety event of interest, a set period of time prior to the event date (washout period) in which the individual may not have experienced the safety event of interest will be defined to more plausibly identify incident cases.

Figure 1. Self-controlled risk interval design to assess general safety events

[figure not shown]
COVID-19 = coronavirus disease 2019.

This study design is appropriate for studying acute events with well-defined risk periods. A strength of the SCRI design is that it avoids confounding due to time-invariant confounders (including prior history of COVID-19 vaccination, which may be challenging to identify in claims administrative data). Additionally, because the SCRI design only includes vaccinated individuals, it avoids misclassification of unexposed status arising from incomplete capture of COVID-19 vaccination in claims data.

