9.2.1. Study population eligibility criteria

9.2.1.1. Population to assess general safety events

Individuals will be eligible for analysis of general safety events (which will use an SCRI design) if they meet the following criteria:

1. Aged ≥ 6 months for at least 1 day during the study observation period.
2. Have received a dose of Pfizer-BioNTech bivalent COVID-19 Vaccine. Note that individuals will be eligible regardless of the brand(s) of any COVID-19 vaccines received before Pfizer-BioNTech bivalent COVID-19 Vaccine.
3. Have had continuous medical and pharmacy insurance coverage for at least 12 months before receipt of the Pfizer-BioNTech bivalent COVID-19 Vaccine, or from birth until receipt of the Pfizer-BioNTech bivalent COVID-19 Vaccine (for individuals aged younger than 12 months at the time of receipt of the vaccine). For children aged younger than 12 months at the time of vaccination, a delay in enrollment (duration to be specified in the SAP) from birth will be allowed.

Additionally, for analysis of each safety event, individuals will be required to meet the following criteria:

4. Have experienced the event of interest during the risk or control intervals (see Section 9.3.2.1 for event-specific risk interval definitions; event-specific control intervals will be defined in the SAP)
5. Did not experience the specific safety event of interest during the pre-event washout period (the event-specific washout periods will be defined in the SAP)
6. Have continuous health plan enrollment from the start of the event-specific risk interval until the end of the event-specific control interval (for individuals who live until the end of the control interval) or until death (for individuals who die before the end of the control interval)

7. Have received no additional doses of COVID-19 vaccine other than Pfizer-BioNTech bivalent COVID-19 Vaccine during the risk interval and no additional doses of COVID-19 vaccine of any brand through the end of the control interval. Additional doses of Pfizer-BioNTech bivalent COVID-19 Vaccine will be allowed during the risk interval to enable the capture of more than 1 dose administered in a short timeframe, as the vaccine is currently approved for use as more than 1 dose in the primary series.

The index date (ie, date of cohort entry) will be the date of receipt of Pfizer-BioNTech bivalent COVID-19 Vaccine.

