9.3.2.1. General safety events

General safety events (which will be assessed using a SCRI design) are listed along with their risk interval definitions in [Table 5](#). Event-specific risk intervals have been defined to reflect a period of potentially increased risk following vaccination. Event-specific control intervals will be defined in a pre-specified period (to be specified in the SAP) following the risk interval. Buffer and control intervals for each outcome will be defined to reflect the baseline risk of the outcome and will take into consideration the duration of the risk interval, the potential seasonality of the outcome, and the recommended timing between the initial bivalent vaccine dose and additional COVID-19 vaccine doses.

Table 5. General safety events

Organ system	Safety event of interest	Risk interval (days following vaccination [Day 0])	Ages to be included in analyses ^a
Cardiac	Myocarditis/pericarditis	1-7	Ages ≥ 6 months
	Acute myocardial infarction	1-28	Ages ≥ 6 months
Neurologic	Acute disseminated encephalomyelitis	1-42	Ages ≥ 6 months
	Bell's palsy	1-42	Ages ≥ 6 months
	Convulsions	1-42	6 months through 4 years
	Encephalomyelitis/encephalitis	1-42	Ages ≥ 6 months
	Guillain-Barré syndrome	1-42	Ages ≥ 6 months
	Transverse myelitis	1-42	Ages ≥ 6 months
Hematologic	Deep vein thrombosis	1-28	Ages ≥ 6 months
	Disseminated intravascular coagulation	1-28	Ages ≥ 6 months
	Immune hemolytic anemia	1-42	Ages ≥ 6 months
	Immune thrombocytopenia	1-42	Ages ≥ 6 months
	Pulmonary embolism	1-28	Ages ≥ 6 months
	Thromboembolic events associated with thrombocytopenia	1-28	Ages ≥ 6 months

090177e19f732934\Approved\Approved On: 14-Dec-2023 13:35 (GMT)

PFIZER CONFIDENTIAL

Table 5. General safety events

Organ system	Safety event of interest	Risk interval (days following vaccination [Day 0])	Ages to be included in analyses ^a
	Thrombotic thrombocytopenic purpura	1-28	Ages ≥ 6 months
	Venous thromboembolism	1-28	Ages ≥ 6 months
	Hemorrhagic stroke	1-28	Ages ≥ 6 months
	Ischemic stroke	1-28	Ages ≥ 6 months
Respiratory	Acute respiratory distress syndrome	1-28	Ages ≥ 6 months
Other system	Anaphylaxis	0-1	Ages ≥ 6 months
	Appendicitis	1-42	Ages ≥ 6 months
	Kawasaki disease	1-42	Ages 6 months through 4 years
	Multisystem inflammatory syndrome	1-42	Ages ≥ 6 months
	Multisystem inflammatory syndrome in children	1-42	Ages < 21 years

COVID-19 = coronavirus disease 2019.

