A study design–related limitation is that the SCRI design (which is planned to assess general safety events) is more sensitive than a cohort design to misspecification of risk and control intervals. However, the SCRI design presents a strong alternative to a cohort design because it inherently adjusts for time-invariant confounders, including prior history of COVID-19 vaccination, which may be difficult to assess in claims data. While the SCRI design can generally be subject to time-varying confounding, the buffer and control intervals for each general safety event will be defined (in the SAP) to minimize this potential source of bias by minimizing each person's total duration of observation. Sensitivity analyses with alternative risk intervals will be considered for outcomes for which signals have been observed in other safety surveillance systems or studies and risk intervals that are not well characterized.

A limitation of the cohort design, which will be used to assess pregnancy and birth outcomes, is the potential for residual or unmeasured confounding, because it is unlikely that the data RPs will have information on all potential confounders. However, the cohort design presents a viable alternative to the SCRI design; unlike the SCRI design, it is suitable to assess safety events for which the risk varies substantially over time (such as spontaneous abortion) and/or the timing of onset is unknown (such as major congenital malformations and small size for gestational age). To address the potential for unmeasured confounding, sensitivity analysis will be performed among pregnant women with a history of monovalent COVID-19 vaccine

PFIZER CONFIDENTIAL

receipt, which may serve as a proxy for health-seeking behaviors and risk factors for pregnancy outcomes.

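### The severe-COVID-19 subgroup pools recent and remote admissions, leaving its self-controlled IRRs open to upward time-varying confounding of unknown size

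*Protocol*

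**What the plan says.** Section 9.7.4 lists among the subgroups for the general safety events "individuals with a recorded history of severe COVID-19 (defined as an inpatient diagnosis in the principal diagnosis position", with a separate coding rule for pregnant women. Table 7 in Section 9.3.3 gives the time frame: "History of severe COVID-19 disease (as of the index date". Section 9.2.1.1 fixes that date: "The index date (ie, date of cohort entry) will be the date of receipt of Pfizer-BioNTech bivalent COVID-19 Vaccine". No section sets a minimum time between admission and vaccination, or a limit on how far back the admission may lie.

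Section 9.1 compares incidence "in a predefined post-vaccination risk interval with that in a self-matched post-vaccination control interval", with a buffer between the two. Section 9.3.2.1 repeats the order: "Event-specific control intervals will be defined in a pre-specified period (to be specified in the SAP) following the risk interval". Table 5 sets the risk intervals at days 1-7, 1-28 or 1-42, apart from anaphylaxis at 0-1.

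Three provisions bear on confounding that changes over time:

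- The washout in Section 9.2.1.1 concerns the outcome only: "Did not experience the specific safety event of interest during the pre-event washout period".
- Section 9.7.3.3 says of the SCRI only that fixed characteristics are not a concern.
- Section 9.9 concedes that "the SCRI design can generally be subject to time-varying confounding" and undertakes to limit this through buffer and control intervals, set in the SAP, that keep each person's observation short.

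The SCRI sensitivity analyses in Table 10 cover alternative risk periods and outcome misclassification. Neither concerns time since COVID-19.

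**The concern.** A self-controlled comparison cancels whatever is constant within a person. It does not cancel a risk that declines between the two intervals. If a COVID-19 admission raises the risk of an event such as venous thromboembolism, stroke or myocardial infarction for some weeks, a person vaccinated soon afterwards carries more of that excess in the risk interval than in the later control interval. The subgroup IRR then mixes any vaccine effect with the tail of the illness.

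This subgroup is selected on that illness and is named in an objective of a study committed to FDA and EMA. An elevated IRR here could be read as a vaccine signal, and no planned analysis would show whether it comes from recent admissions. Because the SCRI analyses only people with events, recent admissions also weigh more than their headcount.

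**Working it through.** **The plan's own figure.** The protocol gives no figure for this bias. Its SCRI power figure is reproduced because the same formula is used at the end. With equal intervals the share of events in the risk interval is p = IRR/(1+IRR), and power = Φ((√n·(p−0.5) − 1.96·0.5)/√(p(1−p))). For n = 80 and IRR 2.0: p = 0.667, √80·0.167 = 1.491, (1.491 − 0.980)/0.471 = 1.083, power 0.86. Table 8 states 0.86.

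**Inputs.** From the protocol: control after risk, with a buffer between; risk intervals of 7, 28 or 42 days; equal interval lengths, as in Section 9.5.1. Assumed, with no support in the protocol: all values for the course of risk, the gaps and the buffer length.

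**Simple mixture, no vaccine effect.** With a share s of recent admissions and event rates a (risk interval) and b (control interval) relative to baseline, IRR = (1−s+s·a)/(1−s+s·b).

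- s = 0.05, a = 2, b = 1.3: 1.05/1.015 = 1.03
- s = 0.15, a = 4, b = 2: 1.45/1.15 = 1.26
- s = 0.30, a = 6, b = 2: 2.50/1.30 = 1.92

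In the middle case 15% of people supply (0.60+0.30)/(1.45+1.15) = 0.90/2.60 = 35% of the events.

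**Explicit decay, no vaccine effect.** Let the hazard be 1 + K·exp(−ln2·t/h), with t days since admission and half-life h. With gap g, interval length L and buffer B = 14 days, the IRR is the integral over (g, g+L) divided by the integral over (g+L+B, g+2L+B).

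Example with K = 4, h = 30, L = 28, g = 14, and λ = ln2/30 = 0.0231:

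- risk interval: 28 + 4·(0.7236 − 0.3789)/0.0231 = 87.7
- control interval: 28 + 4·(0.2742 − 0.1436)/0.0231 = 50.6
- IRR = 87.7/50.6 = 1.73

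Ranges over h = 15, 30 and 60 days, and over all three interval lengths unless one is stated:

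| Scenario | Null IRR |
|---|---|
| Everyone admitted 14 days before, K = 4, 7-day interval | 1.20-1.66 |
| Same, 28-day interval | 1.40-1.86 |
| Same, 42-day interval | 1.53-1.89 |
| Everyone admitted 180 days before, K = 4 | 1.00-1.16 |
| Everyone admitted 365 days before, K = 4 | 1.00-1.02 |
| 10% admitted 7-90 days before, rest no excess, K = 1 | 1.01-1.02 |
| Same, K = 4 | 1.03-1.08 |
| Same, K = 9 | 1.07-1.17 |
| 50% admitted 7-90 days before, K = 4 | 1.13-1.31 |
| Gaps even over two years, K = 4, 28-day interval | 1.06 / 1.10 / 1.12 (h = 15 / 30 / 60) |
| Same, gaps from 90 days only | 1.00 / 1.02 / 1.06 |

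No scenario with declining risk gives an IRR below 1. The last two rows show what a 90-day cut achieves: nearly all of the bias goes if decay is fast, about half if the half-life is 60 days.

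**Consequence for error rates.** With 80 events and the formula above, adding the lower tail, a null IRR of 1.1 (p = 0.524) turns a 5% two-sided error into 0.062 + 0.008, about 7%. A null IRR of 1.3 (p = 0.565) gives 0.212 + 0.001, about 21%.

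**The case against.** The strongest reply is that nothing shows the bias to be material. The history has no lookback limit, so remote admissions dilute recent ones. The explicit decay model with evenly spread gaps gives only 1.06 to 1.12 in the 28-day case. Section 9.9 recognises time-varying confounding and commits to a short observation span, and the interval lengths that govern the contrast are left to the SAP. A long washout would drop people whose event was recorded around the admission. People who defer vaccination while unwell would have low early event rates, which pushes the IRR down. Section 9.7.5 already permits further subgroup analyses, and the SAP may add a recency rule. The subgroup belongs to a secondary objective, and the ENCePP checklist marks hypotheses to be tested as not applicable.

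Most of this stands as a limit on size. It does not remove the mechanism. A shorter span flattens the gradient, but the control interval remains the later one. The washout covers earlier occurrence of the same event, not a raised risk of a first one. The permission in Section 9.7.5 is optional and does not name time since admission. Interval and washout lengths are expressly deferred to the SAP, whereas this subgroup definition is stated without deferral; followed as written, it pools all admissions.

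A reader might infer that the subgroup IRRs are in fact inflated, or that the net bias must be upward. The protocol does not support either: it gives no risk curve and no distribution of gaps, and deferral could act the other way. The value of 1.92 needs 30% recent admissions with six-fold against two-fold rates. Nor do these calculations show any effect on the overall-population results.

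**Conclusion.** The point holds as a vulnerability, not as a demonstrated bias. The definition admits any qualifying admission up to vaccination, the control interval always comes later, and no planned analysis separates recent from remote admissions. For events with an excess still falling after COVID-19, the subgroup IRR is open to upward confounding.

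Its size is unknown. On the assumed values the null IRR is about 1.00 when admissions are mostly remote and about 1.03 to 1.3 with a moderate share of recent ones. Higher values arise only if recent admissions dominate or the post-COVID excess is very large. These figures rest on exponential decay, equal interval lengths, a 14-day buffer and assumed gaps, and they leave out deferral of vaccination.

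One subgroup of secondary objective 1 is affected. The primary objectives and Table 8 are not called into question. The improvement is cheap and worth making.

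**What to change.** Keep the subgroup as defined, so that it still matches the population named in the objective. In Section 9.7.4 and Table 10, pre-specify three additions:

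1. Report the subgroup IRRs also by time from the last qualifying COVID-19 admission to the index date, for example under 90 days versus 90 days or more.
2. Add a sensitivity estimate for the subgroup that leaves out the recent stratum.
3. State that an elevated IRR confined to recent admissions cannot be attributed to the vaccine.

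Replacing the subgroup estimate with a restricted one is not needed and would change the objective's population.

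The work is one date condition on a variable already extracted. It can be settled before the final query, which Section 6 expects in the second quarter of 2026. The price is smaller strata and wider confidence intervals. The 90-day cut is an analysis choice given as an example; if decay is slow it reduces the bias without eliminating it (1.12 to 1.06 at a 60-day half-life), and the report should say so.
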